4.2 Justification for Dose

The starting dose of M4076 for this first-in-human study was determined based on the International Council for Harmonisation (ICH) Guideline S9 'Nonclinical Evaluation for Anticancer Pharmaceuticals' (2009) the FDA guidance (Food and Drug administration: Guidance for Industry: Estimating the Maximum Safe Starting Dose in initial Clinical Trials for Therapeutics in Adult Healthy Volunteers, 2005) and took into consideration the severely toxic dose (STD) and highest non-STD as well as the predicted human exposure and the PK/pharmacodynamic modeling of the predicted pharmacological active dose range in humans.

Completed Good Laboratory Practice 4-week repeat-dose toxicity studies in rats and dogs support the calculation of the starting dose. Applying the common approach of a 10-fold safety margin to the STD10 (> 100 mg/kg/day) in rats (most sensitive species) it corresponds to a human equivalent dose of 96 mg per day (Guidance ICH S9 2010); assuming 60 kg body weight and body surface area correction, which has been rounded to 100 mg.

At the 100 mg M4076 dose, unbound AUC multiples (observed toxicokinetic exposure/predicted human exposure ratio) of approximately 3.0 and 1.5 relative to the toxic dose in 10% of the animals in rat and highest non-severely toxic dose (non-STD) in dog, respectively, are expected based on the predicted human PK. Unbound C_{max} multiples of approximately 6.0 and 5.5 relative to the toxic dose in 10% of the animals in rat and highest non-severely toxic dose in dog, respectively, are estimated based on the predicted human PK. The findings of primary interest in the repeat dose toxicity studies in establishing the starting dose were increased heart rate and lymphatic and hematological toxicity. Based on the nature of these findings and their ability to be monitored clinically, the proposed exposure margins were considered acceptable in the interest of minimizing the exposure of participants to potentially ineffective therapy.

Based on preclinical in vivo studies in settings relevant to pharmacologically evaluate the specific effect of an ATM inhibitor, M4076 is expected to be pharmacologically active at the starting dose of 100 mg.

Part 1B (the preliminary food effect assessment) will be conducted with two single doses of M4076 of the same amount. The dose of M4076 to be administered is planned to be the RDE, although a lower dose may be used at the discretion of the SMC. Based on nonclinical data and predicted high degree of absorption that is expected to be dose-linear up to 600 mg, a clinically relevant food effect is not anticipated. Based on nonclinical repeat dose toxicity and pharmacokinetic studies of M4076, increased exposure as a result of coadministration with food for a single dose is not expected to substantially alter the risk.

See Section 6.6 for information on dose selection and modifications.

4.3 Scientific Rationale for Study Design

The Phase 1, dose-escalation study is designed to establish a safe and tolerable dose of M4076 monotherapy (Part 1A) and to investigate PK, Pd, and early signs of efficacy in participants with advanced solid tumors for which no standard therapy is available.

Rationale for the cross over design for the preliminary food effect assessment (Part 1B): The 2-sequence cross over design, as compared to an alternative parallel design, minimizes the number of study participants required to identify the effect of food on the PK of M4076 since each participant serves as their own control. The selected washout period will sufficiently remove M4076 from the systemic circulation to eliminate the risk of carryover effects which can be deleterious to the study's outcome and interpretation.

Participant involvement in development of the study design was not sought.

4.4 End of Study Definition

End of Study for an Individual Participant: A participant has completed the study if he/she has completed all study parts, including End of Study Intervention Visit and Safety Follow-up Visit (see Section 1.3) or one of the following criteria applies:

- Withdrawal of consent to study
- Lost to Follow-up
- Died

All participants who do not fulfil one of the prior three criteria should be followed until the last participant has completed the Safety Follow-up Visit or transferred to study intervention access outside of this study.

End of Study Overall: The end of the study is defined as the date of completion of study intervention by all participants and all required study activities/visits (including the Safety Follow-up Visit).

Post Study Intervention for an Individual Participant: After the objectives of the study are achieved participants receiving ongoing study intervention may be offered the investigational drug outside of this study under observation of local regulations.

The Sponsor may terminate the study at any time once access to study intervention for participants still benefiting is provisioned via a rollover study, expanded access, marketed product or another mechanism of access, as appropriate.

5 Study Population

The criteria in Sections 5.1 and 5.2 are designed to enroll only participants, who are appropriate for the study; thereby, ensuring the study fulfills its objectives. All relevant medical and nonmedical conditions are considered when deciding whether a participant is suitable for this study.

Prospective approval of protocol deviations to inclusion and exclusion criteria, also known as protocol waivers or exemptions, is not permitted.

Before performing any study assessments that are not part of the participant's routine medical care, the Investigator will confirm that the participant or the participant's legal representative (where allowed by local laws and regulations) has provided written informed consent, as indicated in [Appendix 2](#).

5.1 Inclusion Criteria

The following criteria apply for Part 1A and 1B of this study.

Participants are eligible to be included in the study only if all the following criteria apply:

Age

1. Are ≥ 18 years of age at the time of signing the informed consent.

Type of Participant and Disease Characteristics (including organ function)

2. Patients with advanced solid tumors, for whom no standard of care therapy exists or for whom is not considered sufficiently effective, or who cannot tolerate standard of care.
3. Eastern Cooperative Oncology Group Performance status 0 or 1.
4. Adequate hematological function defined by absolute neutrophil count, $\geq 1.5 \times 10^9/L$, platelet count $\geq 100 \times 10^9/L$, and hemoglobin $\geq 9 \text{ g/dL}$, and without growth factor treatment or blood transfusion within 2 weeks before the study intervention start.
5. Adequate hepatic function defined by total bilirubin level $\leq 1.5 \times$ upper limit of normal (ULN), aspartate aminotransferase level $\leq 3 \times$ ULN, and an alanine aminotransferase (ALT) level $\leq 3 \times$ ULN. For patients with liver metastases, aspartate aminotransferase $\leq 5.0 \times$ ULN, ALT $\leq 5.0 \times$ ULN, and total bilirubin $\leq 3.0 \times$ ULN is acceptable. For patients with Gilbert's disease, total bilirubin $\leq 2.0 \text{ mg/dL}$ or direct bilirubin $\leq 1 \times$ ULN is acceptable.

6. Adequate renal function defined by an estimated glomerular filtration rate > 60 mL/min according to the Cockcroft-Gault equation: (Glomerular filtration rate = $\{(140\text{-age}) \times \text{weight}\}/(72 \times \text{SCr}\}) \times 0.85$ (if female).
7. Participants in Part 1B (the preliminary food effect assessment) must agree to provide paired tumor biopsies if not contraindicated for medical reasons.

Sex

8. Are male and/or female
9. Contraceptive use by males or females will be consistent with local regulations on contraception methods for those participating in clinical studies.

Male participants:

Agree to the following during the study intervention period and for at least 3 months after the last dose of study intervention:

- Refrain from donating sperm.
PLUS, either:
 - Abstain from any activity that allows for exposure to ejaculate.
OR
 - Use a male condom:

When having sexual intercourse with a woman of childbearing potential (WOCBP) and advise her to use a highly-effective contraceptive method with a failure rate of < 1% per year, as described in [Appendix 3](#) since a condom may break or leak.

When engaging in any activity that allows for exposure to ejaculate to another person.

- Male participants must use a male condom with pregnant female partners during the study.

Female participants:

Are not pregnant or breastfeeding, and at least 1 of the following conditions applies:

- Not a WOCBP
OR
- If a WOCBP, use a highly effective contraceptive method (i.e., with a failure rate of < 1% per year), preferably with low user dependency, as described in [Appendix 3](#) for the following time periods:
 - Before the first dose of the study intervention(s), if using hormonal contraception:
 - Has completed at least one 4-week cycle of an oral contraception pill and either had or has begun her menses

OR

- Has used a depot contraceptive or extended cycle oral contraceptive for at least 28 days and has a documented negative pregnancy test using a highly sensitive assay.
- During the intervention period
- After the study intervention period (i.e., after the last dose of study intervention is administered) for at least 6 months after the last dose of study intervention and agree not to donate eggs (ova, oocytes) for reproduction during this period

The Investigator evaluates the effectiveness of the contraceptive method in relationship to the first dose of study intervention

- Have a negative urine pregnancy test, as required by local regulations, within 24 hours before the first dose of study intervention
- Women should not breastfeed during the study and for at least 1 month after the study period, (i.e., after the last dose of study intervention is administered).

Additional requirements for pregnancy testing during and after study intervention are in Section 8.3.5.

The Investigator reviews the medical history, menstrual history, and recent sexual activity to decrease the risk for inclusion of a female with an early undetected pregnancy.

Informed Consent

10. Capable of giving signed informed consent, as indicated in [Appendix 2](#), which includes compliance with the requirements and restrictions listed in the informed consent form (ICF) and this protocol.

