Cytopenia, lymphopenia +/- infections	Refer to Section 6.1 of the M4076 IB.	Exclusion of participants with insufficient bone marrow function. Regular monitoring of laboratory evaluations for hematology and vital signs. Continuous monitoring of AEs with clinical management as indicated, including study intervention interruption, dose modification or discontinuation.
Increased heart rate	Refer to Section 6.1 of the M4076 IB.	Exclusion of subjects with significant cardiac conduction abnormalities. Regular monitoring of ECG and vital signs. Continuous monitoring of adverse events with clinical management as indicated, including study intervention interruption, dose modification or discontinuation.
Birth defects and abortions	In vitro and in vivo genotoxicity investigations showed M4076 to cause genotoxicity. Refer to Section 4.3.3 of M4076 IB.	Strict contraception for participants and their partners as inclusion criteria, during treatment, and thereafter 6 months for females and 3 months for males, including refraining from sperm donations.
Risks associated with drug-drug interactions	No formal drug-drug interaction studies have been conducted with M4076 in humans. Refer to Section 4.2.9 of M4076 IB.	Concomitant administration with strong inhibitors or inducers of CYP3A4 or P-glycoprotein agents is prohibited. Concomitant administration with sensitive clinical substrates of UGT1A1 or P-gp, with potentially narrow therapeutic index or known safety risks are prohibited, specifically irinotecan, digoxin, and oral

		direct thrombin inhibitors. Clinical substrates of CYP3A4 with narrow therapeutic index are prohibited. Clinical sensitive substrates and moderate inhibitors of CYP3A4 should be avoided and if permitted, should be used with caution.
Study Procedures		
Assessment	Summary of Data/Rationale for Risk	Mitigation Strategy
Blood Sampling	Blood sampling is required for participants as detailed in the Schedule of Activities and is considered essential for the study's scientific objectives. Blood sampling carries a risk of AEs including pain, bruising, bleeding, redness and swelling of the site/vein, and infection.	Minimization of blood sampling was thoughtfully considered during protocol development weighing risk to participants versus achievement of the study's scientific objectives.

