Appendix 3 Contraception

Definitions:

Woman of Childbearing Potential (WOCBP)

A woman is considered fertile following menarche and until becoming postmenopausal unless permanently sterile, as specified below.

If fertility is unclear (e.g., amenorrhea in adolescents or athletes) and a menstrual cycle cannot be confirmed before the first dose of study intervention, consider additional evaluation.

A WOCBP is not:

1. Premenarchal
2. A premenopausal female with 1 of the following:
 - Documented hysterectomy
 - Documented bilateral salpingectomy
 - Documented bilateral oophorectomy

Documentation can come from the site personnel's review of the female's medical records, medical examination, or medical history interview.

For a female with permanent infertility due to an alternate medical cause other than the above, (e.g., mullerian agenesis, androgen insensitivity), investigator discretion applies to determine study entry.

3. A postmenopausal female
 - A postmenopausal state is defined as no menses for 12 months without an alternative medical cause.
 - A high follicle-stimulating hormone (FSH) level in the postmenopausal range may be used to confirm a postmenopausal state in a female not using hormonal contraception or hormonal replacement therapy (HRT). However, in the absence of 12 months of amenorrhea, more than 1 FSH measurement is required in the postmenopausal range.
 - A female on HRT and whose menopausal status is in doubt will be required to use one of the non-estrogen hormonal highly effective contraception methods if she wishes to continue her HRT during the study. Otherwise, she must discontinue HRT to allow confirmation of postmenopausal status before study enrollment.

Contraception Guidance:

CONTRACEPTIVES ALLOWED DURING THE STUDY INCLUDE:

Highly Effective Methods That Have Low User Dependency

- Implantable progestogen-only hormone contraception associated with inhibition of ovulation
- Intrauterine device (IUD)
- Intrauterine hormone-releasing system (IUS)
- Bilateral tubal occlusion
- Vasectomized partner: a highly effective contraceptive method provided that the partner is the sole sexual partner of a WOCBP and the absence of sperm has been confirmed. Otherwise, use an additional highly effective method of contraception. The spermatogenesis cycle is approximately 90 days.

Highly Effective Methods That Are User Dependent

- Combined (estrogen- and progestogen-containing) hormonal contraception associated with inhibition of ovulation

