 - Oral
 - Intravaginal
 - Transdermal
 - Injectable
- Progestogen-only hormone contraception associated with inhibition of ovulation
 - Oral
 - Injectable
- Sexual abstinence: a highly effective method **only** if defined as refraining from intercourse during the entire period of risk associated with the study intervention. The reliability of sexual abstinence is evaluated in relation to the duration of the study.

Acceptable Methods

- Progestogen-only oral hormonal contraception where inhibition of ovulation is not the primary mode of action
- Male or female condom with or without spermicide. Male condom and female condom cannot be used together (due to risk of failure with friction)
- Cervical cap, diaphragm, or sponge with spermicide
- A combination of male condom with either cervical cap, diaphragm, or sponge with spermicide (double-barrier methods)

Contraceptive use by men or women is consistent with local regulations regarding the use of contraceptive methods for those participating in clinical studies.

Highly effective methods have a failure rate of < 1% per year when used consistently and correctly. Typical use failure rates differ from those when used consistently and correctly.

Hormonal contraception may be susceptible to interaction with the study intervention(s), which may reduce the efficacy of the contraceptive method. As such, male condoms must be used in addition to hormonal contraception. If locally required, in accordance with Clinical Trial Facilitation Group guidelines, acceptable contraceptive methods are limited to those which inhibit ovulation as the primary mode of action.

Acceptable methods are considered effective, but **not** highly effective (i.e., have a failure rate of $\geq 1\%$ per year). Periodic abstinence (calendar, symptothermal, post-ovulation methods), withdrawal (coitus interruptus), spermicides only, and lactational amenorrhoea method are **not** acceptable methods of contraception.

Appendix 4 Adverse Events: Definitions and Procedures for Recording, Evaluating, Follow-up, and Reporting**AE Definition****AE Definition**

- An AE is any untoward medical occurrence in a patient or clinical study participant, temporally associated with the use of study intervention, whether considered related to the study intervention or not.

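### Criterion 9 requires contraception with a failure rate below 1% per year, but the Appendix 3 list of allowed methods it cites includes a block rated at 1% or more

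*Protocol*

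**What the plan says.** Criterion 9 in Protocol Section 5.1 applies to female participants as follows: "If a WOCBP, use a highly effective contraceptive method (i.e., with a failure rate of < 1% per year), preferably with low user dependency". It cites Appendix 3 for the methods. For a male participant with a WOCBP partner, the same criterion asks him to "advise her to use a highly-effective contraceptive method with a failure rate of < 1% per year, as described in" Appendix 3.

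Appendix 3 opens its guidance with the heading "CONTRACEPTIVES ALLOWED DURING THE STUDY INCLUDE". Three blocks follow: highly effective with low user dependency, highly effective but user dependent, and Acceptable Methods. The third includes "Progestogen-only oral hormonal contraception where inhibition of ovulation is not the primary mode of action" and "Cervical cap, diaphragm, or sponge with spermicide", as well as condoms and double-barrier combinations. The explanatory text after the list puts highly effective methods below 1% failures per year and the Acceptable Methods block at 1% or more. The same text says of hormonal methods: "As such, male condoms must be used in addition to hormonal contraception".

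Table 5 in Section 2.3.1 records that M4076 was genotoxic in vitro and in vivo. Against birth defects and abortions it gives this mitigation: "Strict contraception for participants and their partners as inclusion criteria, during treatment, and thereafter 6 months for females and 3 months for males".

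**The concern.** The eligibility criterion and the appendix it relies on should give the same answer for the same woman. For a WOCBP whose only method comes from the third block, they do not. The criterion's threshold excludes her, while her method stands on a list headed as allowed during the study.

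The reproductive-risk control depends on this wording. Table 5 does not describe contraception as general advice; it places it among the inclusion criteria. If a site checks eligibility against the list, the control actually applied is weaker than the one Table 5 describes. There is also a consequence for the data. Section 5 of the protocol permits no eligibility waivers, and SAP Section 10.2.1 counts dosing a participant who did not meet enrolment criteria as an important protocol deviation. A site following the list in good faith could create such a deviation.

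**Working it through.** The plan states no figure to reproduce and no formula applies. The check sets the passages side by side.

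1. **Threshold.** Criterion 9 accepts, for a WOCBP, only methods with a failure rate below 1% per year.
2. **Pointer.** Criterion 9 sends the reader to Appendix 3 as a whole. It names no block within it.
3. **Scope of the heading.** "CONTRACEPTIVES ALLOWED DURING THE STUDY INCLUDE" stands above all three blocks, so on its face every entry in the third block is allowed.
4. **The appendix's own rating.** Highly effective means below 1% per year; the third block is at 1% or more per year. These categories are disjoint, so no method can belong to both.
5. **Does Appendix 3 rule the third block out for this study?** It says the block is not highly effective, but not that the block fails criterion 9. Two other sentences lean towards the block being usable. One restricts acceptable methods to those acting mainly by inhibiting ovulation, but only where local rules require it. The other lists methods that are not acceptable (periodic abstinence, withdrawal, spermicide alone, lactational amenorrhoea) and leaves the third block off that list. These are indications rather than proof, because the local-requirement sentence is worded generally.
6. **Which entries show the conflict most clearly?** "Progestogen-only oral hormonal contraception where inhibition of ovulation is not the primary mode of action" and "Cervical cap, diaphragm, or sponge with spermicide" are methods a WOCBP might use alone, and nothing labels them as add-ons. The male condom is different. Criterion 9 requires it of male participants who do not abstain, and Appendix 3 requires it alongside hormonal contraception, so it has a proper place on a list of allowed methods.
7. **Whom does the conflict bind?** The below-1% duty is an eligibility condition for female participants who are WOCBP. For male participants the partner's method is a matter of advice, although that advice points to the same list.

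**The case against.** The best defence is that the cross-reference resolves itself. Criterion 9 asks for a highly effective method, and Appendix 3 labels two blocks with that term and says the third does not meet it. Eligibility is governed by Section 5.1, where all criteria must be met, and the Investigator must evaluate the method's effectiveness. A careful site would therefore use only the first two blocks. That reading is available, and criterion 9 is clear when read alone. It does not remove the inconsistency, because the heading says allowed, no sentence limits the third block to add-on use, and step 5 of the check shows text pointing the other way.

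Three stronger readings are tempting, and the documents support none of them.

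- A reader might infer that every entry in the third block conflicts with criterion 9. The male condom's roles for men and as an add-on rule that out. The conflict concerns a third-block method as a WOCBP's sole method.
- A reader might infer a second contradiction from "As such, male condoms must be used in addition to hormonal contraception", which criterion 9 does not repeat. This is an added condition that the reference to Appendix 3 can carry into the criterion, and both texts can be met together.
- A reader might use the 105 days/15 weeks in Section 4.1 as treatment time and calculate a risk from it. The protocol gives that figure as estimated time on study. Treatment continues until progression or another stopping event, and the documents give only two failure-rate categories, so no added risk can be quantified.

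**Conclusion.** The point holds as an internal inconsistency between criterion 9 and Appendix 3. For a WOCBP relying solely on a third-block method, the criterion says below 1% per year, while the list allows a method the appendix rates at 1% or more and does not say it is insufficient here. The passages must be reconciled because Table 5 relies on the criterion to control the reproductive risk of a genotoxic drug.

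The practical size is probably small but cannot be stated. Section 9.2 plans approximately 40 participants, and the documents do not say how many would be WOCBP or which methods they use. No estimate, error rate or analysis set definition changes. The conclusion assumes only that a site may read the Appendix 3 heading at face value. It does not assume that any site has done so, and it takes no position on which contraceptive rule is right.

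**What to change.** Reconcile Section 5.1, criterion 9, with Appendix 3. Appendix 3 should state which of its blocks satisfy criterion 9 for a WOCBP, and its heading on allowed methods should give the same answer as the criterion. The sponsor may do this by changing either passage; the choice of rule is the sponsor's. Optionally, for clarity, criterion 9 could cross-refer to the appendix's condition on condoms with hormonal contraception.

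The cost is a few lines of wording and no new tests or visits. Depending on how the passages are reconciled, a few candidates may be affected.
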